6.1.2. Imputation

Missing data will not be imputed. If relationship of AEs to the study vaccine could not be derived (i.e. missing or unknown) it will be considered as unknown, for analysis purposes. Solicited local AEs will be considered as related with the use of study vaccine. Missing relationships will not be imputed.

Period allocation of AEs is defined in Attachment 1.

6.1.3. Analysis

AEs (solicited and unsolicited) will be tabulated by presenting the number and percentage of participants having at least one of the observed AEs.

The unsolicited AEs will be summarised by System Organ Classification (SOC) and Preferred Term (PT). The solicited AEs will be summarized by class (local, systemic) and PT. For solicited as well as unsolicited AEs, tables focussing on severity and relatedness to vaccine will be created.

SAEs, AEs with fatal outcomes, AEs leading to permanent discontinuation of vaccine, Grade 3 AEs and AESIs will be listed. Tables, summarizing all those parameters will also be created.

For the solicited local and systemic AEs, the duration and time to onset of the events will also be summarized. If a participant experience more than one occurrence of a solicited event, the maximum duration of the events will be used. The time to first onset is defined as:

[date of first onset – reference date+1]

The reference date is the start date of each vaccination period. Duration and time to onset of AEs will be expressed in days.

Summaries, listings, datasets, and/or participant narratives may be provided as appropriate, for those participants who die, or experience a SAE.

The analysis of AEs will be based on MeDRA coded terms as provided in the clinical database.

A listing of all SAEs during the study period will be provided. A listing of all AESIs (if flagged in the database) will be presented as well.

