8.3.2 Study Pausing Rules

The investigators and the sponsor's medical safety officer or delegate will review the safety of enrolled participants on an ongoing basis and will halt vaccination of further participants in case any of the pre-specified pausing rules described in this section are met. The sponsor's medical safety officer or delegate will be involved in all discussions and decisions.

If any of the following events occur in any participant who received the study intervention, the site investigator will halt the vaccination of further participants in the study, and the sponsor's medical safety officer or delegate will be notified immediately:

1. Death of a participant considered related to the study intervention, or if the causal relationship to the study intervention cannot be excluded; *OR*
2. One or more participants experience a SAE (solicited or unsolicited) that is determined to be related to study intervention; *OR*
3. One or more participants experience anaphylaxis or generalized urticaria within 24 hours of vaccination, clearly not attributable to causes other than vaccination with the study intervention.

To enable prompt response to a situation that could trigger pausing rules, the investigator should notify the sponsor's medical safety officer or delegate immediately and no later than 24 h after becoming aware of any related AE of grade 3 or above AND update the CRF with relevant information on the same day the AE information is collected. A thorough analysis of all grade 3 cases will be carried out by the sponsor's medical safety officer or designee, irrespective of whether the criteria for pausing the study are met. Based on the pausing criteria, the sponsor's medical safety officer or delegate then decides whether a study pause is warranted. All investigator(s) will be notified immediately in case of a study pause. The sponsor's medical safety officer or delegate is responsible for the immediate notification of independent medical reviewer and coordination of a meeting with the independent medical reviewer in case of a study pause.

The sponsor's medical safety officer or delegate or the investigator (upon consultation with the sponsor's medical safety officer or delegate) may contact the independent medical reviewer in any case in which, in their professional opinion, the safety of the participants or the reliability of the data could be affected.

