6.1.1. Definitions

Solicited AEs are precisely defined events (local and systemic) that participants are specifically asked about and which are noted by participants or study staff in the diary. All the other AEs are considered unsolicited. Please refer Clinical Protocol ⁽¹⁾, Section 11 for further details.

Causality

Solicited AEs will be considered as related to the study vaccine. Unsolicited AEs will be considered to be related to the use of the study vaccine if attribution is possibly, probably or very likely. An AE will be considered not related to the use of the study vaccine if the attribution is not related or doubtful. Please refer to Clinical Protocol ⁽¹⁾, Section 11.1.2 for further details.

Severity

The severity of AEs is classified as mild, moderate, severe or potentially life threatening. Please refer to CTP ⁽¹⁾, section 11.1.3 for further details. Solicited events that are graded less than mild, are not considered as AE.

For induration/swelling both the diameter and grading as reported by the investigator are reported in the eCRF. Diameter will be used to derive toxicity grading. The highest grading should be used when both the diameter grading and the investigator-reported grading are available.

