6.2.1. Analysis Methodology

Laboratory data will be analysed based on the full analysis set. The data will be summarized by the type of laboratory test.

Unless specified otherwise, percentages are calculated versus the number of participants in the analysis set with non-missing data for the parameter, period (if applicable) and vaccination group under evaluation.

Tabulation of the highest emerging graded abnormalities per period and overall will be provided. Special attention will be given to participants who develop Grade 3 toxicities. For tests that have no grading, tabulations of the worst emerging abnormalities (below/above) will be performed.

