AE2: start date: 08JUL2021 - stop date: 18JUL2021

AE1 will be attributed to the screening period and AE2 to the Post-boost dose period.

Example for the above scenario 3

AE1: start date: 18JUL2021- stop date: 28JUL2021

AE2: start date: 28JUL2021- stop date: 08AUG2021

As AE1 starts in the active period (Post-boost dose) and overlaps with AE2 which starts in a non-active period (Post-boost dose FU), this AE is considered as a single AE in the AE analysis starting on 18JUL2021 and ending on 08AUG2021 and is attributed to the post-boost dose period.

2. Toxicity Grading Scale for Healthy Paediatric Participants (older than 3 months) Enrolled in Preventive Vaccine Clinical Trials

Adapted from: DMID° Pediatric Toxicity Tables (November 2007, draft). For adverse events not included in the tables below, refer to the severity criteria guidelines. Reference source not found. Local lab references take preference over the DMD table and the different grades. The abbreviations used in the following tables are: LLN: lower limit of normal; IV: intravenous; ULN: upper limit of normal.

LOCAL REACTIONS				
	Grade 1	Grade 2	Grade 3	Grade 4
Tenderness	Mild discomfort to touch; minimal to no limitation of use of limb	Notable discomfort to touch; Greater than minimal limitation of use of limb	Significant discomfort at rest; Severe limitation of use of limb	Hospitalization or ER visit for treatment
Erythema	<10 mm	10-25 mm	26-50 mm	>50 mm or any grade 3 with hospitalization or ER visit for treatment
Swelling	<10 mm	10-25 mm	26-50 mm	>50 mm or any grade 3 with hospitalization or ER visit for treatment
HEMATOLOGY				
	Grade 1	Grade 2	Grade 3	Grade 4
Hemoglobin for children greater than 3 months and less than 2 years of age	9.0-9.9 gm/dL	7.0-8.9 gm/dL	<7.0 gm/dL	Cardiac Failure secondary to Anemia

Hemoglobin for children greater than 2 years of age	10.0-10.9 gm/dL	7.0-9.9 gm/dL	<7.0 gm/dL	Cardiac Failure secondary to Anemia
Absolute Neutrophil Count	750-1200/mm3	400-749/mm3	250-399/mm3	<250/mm3
Platelets	75,000-99,999/mm3	50,000-74,999/mm3	25,000-49,999/mm3	<25,000/mm3
Prothrombin Time (PT)	1.1-1.2 x ULN	1.3-1.5 x ULN	1.6-3.0 x ULN	>3.0 x ULN
Partial Thromboplastin Time (PTT)	1.1-1.6 x ULN	1.7-2.3 x ULN	2.4-3.0 x ULN	>3.0 x ULN

GASTROINTESTINAL				
	Grade 1	Grade 2	Grade 3	Grade 4
Bilirubin (Fractionated bilirubin test must be performed when total bilirubin is elevated)				

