Bilirubin for children greater than 3 months of age (when accompanied by any increase in other liver function test)	1.1- <1.25 x ULN	1.25- <1.5 x ULN	1.5-1.75 x ULN	>1.75 x ULN
Bilirubin for children greater than 3 months of age (when other liver functions are in the normal range)	1.1- <1.5 x ULN	1.5- <2.0 x ULN	2.0-3.0 x ULN	>3.0 x ULN
AST (SGOT)	1.1- <2.0 x ULN	2.0- <3.0 x ULN	3.0-8.0 x ULN	>8.0 x ULN
ALT (SGPT)	1.1- <2.0 x ULN	2.0- <3.0 x ULN	3.0-8.0 x ULN	>8.0 x ULN
GGT	1.1- <2.0 x ULN	2.0- <3.0 x ULN	3.0-8.0 x ULN	>8.0 x ULN
Pancreatic Amylase	1.1- 1.4 x ULN	1.5- 1.9 x ULN	2.0-3.0 x ULN	>3.0 x ULN
Uric Acid	7.5-9.9 mg/dL	10.0-12.4 mg/dL	12.5-15.0 mg/dL	>15.0 mg/dL
Loss of Appetite	Feeding minimally reduced	Feeding reduced by more than 50% of normal for the child	Refusing all feeds	No solid or liquid taken orally for in the last 24 hours; requires intravenous fluids
Diarrhea	Change in consistency of stools OR increase of 1-3 stools over baseline per 24-hour period	liquid/watery stools OR increase of 4 to 6 stools over baseline per 24-hour period	Increase of ≥ 7 stools over baseline per 24-hour period	Requires IV fluid resuscitation and electrolytes repletion OR hypotensive shock

Constipation	Slight change in consistency and/or frequency of stools	Hard, dry stools with a change in frequency	Intestinal obstruction accompanied with abdominal pain	Hospitalization; Severe abdominal distention and vomiting accompanied with severe abdominal pain
Vomiting	1 episode/ day (24h)	2-3 episodes per day (24h)	4-6 episodes per day (24h)	Greater than 6 episodes per day (24h) OR intractable vomiting

ELECTROLYTES				
	Grade 1	Grade 2	Grade 3	Grade 4
Creatinine				
3 Months – 2 Years of age	0.6-0.8 x ULN	0.9-1.1 x ULN	1.2-1.5 x ULN	>1.5 x ULN
2 Years – 3 Years of age	0.7-1.0 x ULN	1.1-1.6 x ULN	1.7-2.0 x ULN	>2.0 x ULN
Hypernatremia	----	145-149 mEq/L	150-155 mEq/L	>155 mEq/L or abnormal sodium AND mental status changes
Hyponatremia	----	130-135 mEq/L	129-124 mEq/L	<124 mEq/L or abnormal sodium AND mental status changes
Hyperkalemia	5.0-5.9 mEq/L	6.0-6.4 mEq/L	6.5-7.0 mEq/L	>7.0 mEq/L or abnormal potassium AND cardiac arrhythmia
Hypokalemia	3.0-3.5 mEq/L	2.5-2.9 mEq/L	2.0-2.4 mEq/L	<2.0 mEq/L or abnormal potassium AND cardiac arrhythmia
Hypercalcemia	10.5-11.2 mg/dL	11.3-11.9 mg/dL	12.0-12.9 mg/dL	>13.0 mg/dL
Hypocalcemia	7.8-8.4 mg/dL	7.0-7.7 mg/dL	6.0-6.9 mg/dL	>6.0 mg/dL

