Hypomagnesemia	1.2-1.4 mEq/L	0.9-1.1 mEq/L	0.6-0.8 mEq/L	<0.6 mEq/L or abnormal magnesium AND cardiac arrhythmia
hypoglycemia	55-65 mg/dL	40-54 mg/dL	30-39 mg/dL	<30 mg/dL or abnormal glucose AND mental status changes
Hyperglycemia	116-159 mg/dL	160-249 mg/dL	250-400 mg/dL	>400 mg/dL or ketoacidosis
Proteinuria	Tr-1+ or <150 mg/day	2+ or 150-499 mg/day	3+ or 500-1000 mg/day	4+ or Nephrotic syndrome >1000 mg/day
Hematuria	Microscopic <25 cells/hpf	Microscopic >25 cells/hpf	Gross hematuria	Hospitalization; Lifethreatening consequences

NEUROLOGIC				
	Grade 1	Grade 2	Grade 3	Grade 4
Irritability	Easily consolable; minimal or no interference with activity. Episodes of continuous crying <60 min.	Difficult to console. Episodes of continuous crying >60 min <120 min	Inconsolable, prevents daily activity. Episodes of continuous crying >120 min	Hospitalization or ER visit for treatment
Decreased Activity	Minimal decrease in alertness, minimal or no interference with activity	Some interference with activity, slightly subdued	unable to achieve normal level of alertness, lethargic	ER visit or hospitalization for treatment or life-threatening consequences
Neuropathy/ Lower Motor Neuropathy	----	Mild transient Paresthesia only	Persistent or progressive paresthesia, burning sensation in feet, or mild dysesthesia; no weakness; mild to moderate deep tendon reflex changes; no sensory loss	Onset of significant weakness, decrease or loss of DTRs, sensory loss in "stocking glove" distribution, radicular sensory loss, multiple cranial nerve involvement; bladder or bowel dysfunction, fasciculations, respiratory embarrassment from chest wall weakness.
Myopathy or Neuromuscular Junction Impairment	Normal or mild (<2 x ULN) CPK elevation	Mild proximal weakness and/or atrophy not affecting gross motor function. Mild myalgias, +/- mild CPK elevation (<2 x ULN)	Proximal muscle weakness and/or atrophy affecting motor function +/- CPK elevation; or severe myalgias with CPK >2 x ULN;	Onset of myasthenia-like symptoms (fatigable weakness with external, variable ophthalmoplegia and/or ptosis), or neuromuscular junction blockade (acute paralysis) symptoms
OTHER				
	Grade 1	Grade 2	Grade 3	Grade 4
Fever/pyrexia	38.0 - 38.4 °C or 100.4 - 101.1 °F	38.5 - 38.9 °C or 101.2 - 102.0 °F	39.0 - 40.0 °C or 102.1 - 104.0 °F	Greater than 40 °C or 104.0 °F
Acute allergic reaction	Pruritus without Rash	Pruritic Rash	Mild Urticaria	Severe Urticaria Anaphylaxis, Angioedema

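### SAP 6.1.3 lists and summarises Grade 3 adverse events on a four-grade scale, so a non-serious Grade 4 reaction can fall outside that listing and its summary table

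*SAP*

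**What the plan says.** SAP 6.1.3 defines the listing of notable adverse events: "SAEs, AEs with fatal outcomes, AEs leading to permanent discontinuation of vaccine, Grade 3 AEs and AESIs will be listed". The next sentence commits to tables that summarise those same categories. For laboratory data, SAP 6.2.1 says: "Special attention will be given to participants who develop Grade 3 toxicities". Neither section adds a phrase for grades above 3.

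The scale does go above 3. SAP 6.1.1 states: "The severity of AEs is classified as mild, moderate, severe or potentially life threatening", which gives the fourth level its own name, separate from severe. SAP Attachment 2, the paediatric toxicity table, has a Grade 4 column throughout. For measured local reactions, SAP 6.1.1 adds: "Diameter will be used to derive toxicity grading", and the higher of the diameter-derived and investigator grades is kept.

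The protocol uses both forms in one paragraph. Section 8.3.2 requires the site to notify related events from Grade 3 upwards, and then says: "A thorough analysis of all grade 3 cases will be carried out".

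**The concern.** A severity listing should include everything at or above its threshold. With a rule that names one grade, a child with 45 mm of swelling is listed, and a child with 55 mm and no hospital contact may not be. The ordering is then wrong at the top of the scale.

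This matters because the listing shows a reader individual children in an uncontrolled study of about 50. A programmer who selects records with grade equal to 3 would be following the plan as written, and nothing in SAP 6.1.3 would flag the omission.

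**Working it through.** The plan gives no figure to reproduce here. The check sets the listing rule beside the Grade 4 definitions, the other ways into the listing, and the remaining outputs.

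**Step 1. Can Grade 4 be reached without admission?** From SAP Attachment 2:

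| Item | Grade 3 | Grade 4 | Admission needed for Grade 4? |
|---|---|---|---|
| Erythema, swelling | 26–50 mm | ">50 mm or any grade 3 with hospitalization or ER visit for treatment" | No; diameter alone is enough |
| Fever | 39.0–40.0 °C | "Greater than 40 °C or 104.0 °F" | No |
| Vomiting | 4–6 episodes in 24 h | "Greater than 6 episodes per day (24h) OR intractable vomiting" | No |
| Neutrophils | 250–399/mm³ | below 250/mm³ | No |

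Tenderness also reaches Grade 4 with an emergency-room visit, which is not an inpatient stay.

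**Step 2. Would another listing category catch these events?**

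- *SAE.* The definition in protocol 11.1.1 contains no grade. The events above are serious only if another criterion applies, chiefly the judgement that the event is medically important.
- *Fatal outcome.* Not relevant to a non-serious event.
- *Discontinuation of vaccine.* Each child receives a single dose (protocol section 6), so this category can catch almost nothing.
- *AESI.* Limited to thrombotic events and symptomatic thrombocytopenia (SAP 6.1.1.2). It covers symptomatic low platelets, but not swelling, fever or vomiting.

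**Step 3. Does the record structure help?** SAP Attachment 3 creates a new record whenever the grade of a solicited event changes. A swelling that is 55 mm on one day and 40 mm on another has a Grade 3 record, so the child is listed, although the Grade 4 record itself is not. A reaction that never has a Grade 3 record is missed altogether. Because the higher of the two grades is kept for measured local reactions, an investigator grade of 3 does not bring a 55 mm swelling back into the listing.

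**Step 4. Where do Grade 4 events still appear?** SAP 6.1.3 also plans tables by severity for solicited and unsolicited events, and severity has four levels. SAP 6.2.1 tabulates the highest emerging laboratory grade. Protocol 10.4 provides a listing of the most severe laboratory abnormalities, although SAP 6.2.1 does not repeat it.

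**Step 5. Size within the affected outputs.** Inputs: about 25 children per age group and about 50 in all (protocol 10.2, SAP 1.4). One omitted child is 1/25 = 0.04, or 4% of an age group, and 1/50 = 0.02, or 2% overall.

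**The case against.** The strongest reply is that little is lost. The same section plans severity tables that count Grade 4, and the laboratory tabulation is by highest grade. Events outside the toxicity table need hospitalisation or in-patient care to be Grade 4 (protocol 11.1.3), so they would normally be listed as SAEs. A very low platelet count, if symptomatic, is listed as an AESI. Many large local reactions will pass through Grade 3 on another diary day. Protocol 8.3.2 itself moves between the two phrasings, which suggests loose drafting and not a decision to leave Grade 4 out. All of this stands, and it limits the point to one listing and its table.

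The reply does not remove the point. The optional listings and narratives in SAP 6.1 may or may not be produced, and they refer to severe events, which is the label for Grade 3. The version of that sentence in SAP 6.1.3 covers only deaths and SAEs.

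A reader might go further and infer that the worst reactions vanish from the safety analysis, or that the severe rate is understated against the programme's earlier figure of under 2% for Grade 3 solicited events (protocol 1.1). The documents support neither reading. Step 4 answers the first. On the second, the documents do not say whether the earlier figure includes Grade 4; if it does not, a Grade 3 row is the like-for-like comparison. Nor do the documents call this listing the main safety result.

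**Conclusion.** The point holds for the participant-level listing in SAP 6.1.3 and its matching summary table. As written, both can omit a non-serious Grade 4 reaction that has no Grade 3 record, while including a milder one. Each such child is 4% of an age group or 2% of the study in those two outputs. Grade 4 events remain in the severity tables and the laboratory tabulation. The special-attention sentence in SAP 6.2.1 defines no output of its own, so changing it is for consistency only.

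Two assumptions matter. First, the rule is applied literally; if the programmers already read it as Grade 3 and above, only the text needs correcting. Second, solicited reactions are graded on SAP Attachment 2. Protocol 11.1.3 excepts solicited events from its use of the toxicity table without naming another scale, but Attachment 2 grades local reactions by diameter, as SAP 6.1.1 requires. If its general guideline applied to fever and vomiting instead, Grade 4 would need in-patient care and those two examples would fall away.

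**What to change.** - In SAP 6.1.3, replace *Grade 3 AEs* with *AEs of Grade 3 or higher*, for both the listing and the summary table.
- In SAP 6.2.1, use *Grade 3 or higher toxicities*, for consistency.
- In protocol 8.3.2, the notification threshold and the description of the cases to be analysed differ. The sponsor should reconcile the two phrases.

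The SAP changes are a few words and need no new data or method. The only downside is that the reported severe-event count may be slightly higher. If a row comparable with earlier Grade 3 figures is wanted, Grades 3 and 4 can be shown separately within the table.

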6.2. Clinical Laboratory Tests

In case a laboratory result is *censored* (no numeric value is available, but only a verbatim term) then a numeric value will be imputed by a value exceeding the cut-off value with one unit. (<x: subtract 1 unit from x, >x: add 1 unit to x)

Toxicity grades will be determined according to the scales in Attachment 2 and 3. DMID Paediatric toxicity scale will be used. In case no toxicity grades are defined for a test, the abnormalities (below/ above normal range) will be used. In determining toxicity grades, the following rules will be applied:

Highest grades/worst abnormalities are determined over the entire period.

The abnormalities “abnormally low” and “abnormally high” are considered equally important and both abnormalities are shown in tables. (This mean that the sum of percentages can exceed 100%)

If a laboratory value falls within the grading as specified in the grading table but also within the local laboratory normal limits, the value is considered as normal or Grade 0.

Laboratory results falling between the grading scales will be allocated to the adjacent worst case grade (because the scale for some parameters in the grading table is not continuous as there may be zones where toxicity grades definitions do not exist)

Definition emerging abnormalities following vaccination: An abnormality (toxicity grade or abnormality based on normal ranges) will be considered as emerging in a particular period if it is worse than baseline value. A shift from “abnormally low” at baseline to “abnormally high” post baseline or vice versa is also emerging.

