8.1.3 Vaccination Period

Rationale: Minor editorial changes have been made.

Throughout the document

Rationale: References have been updated.

REFERENCES

SYNOPSIS

TITLE

An open label study to evaluate the safety and immunogenicity of an Ad26.ZEBOV booster dose in children previously vaccinated with the Ad26.ZEBOV and MVA-BN-Filo vaccine regimen.

RATIONALE

Over 600 children have received the adenovirus serotype 26 expressing the Ebola virus Mayinga glycoprotein (Ad26.ZEBOV), modified Vaccinia Ankara Bavarian Nordic vector expressing multiple filovirus proteins (MVA-BN-Filo) Ebola vaccine regimen in the EBL2002 and EBL3001 clinical trials. The vaccine regimen was well-tolerated and highly immunogenic in children; however, the durability of vaccine-induced immune responses is not known. In adults previously vaccinated with the Ad26.ZEBOV and MVA-BN-Filo regimen, a booster vaccination with Ad26.ZEBOV was safe and induced a strong anamnestic response within seven days of the booster vaccination. It is important to establish if a booster dose of Ad26.ZEBOV is safe and immunogenic also in children, as this can guide the clinical use of the Ad26.ZEBOV, MVA-BN-Filo vaccine regimen in this age group. For example, it could support the strategy of boosting immunised children at the start of an Ebola outbreak.

STUDY OBJECTIVES AND HYPOTHESIS

This study aims to evaluate the safety and immunogenicity of an Ad26.ZEBOV booster dose in healthy children who were previously (>2 years) vaccinated with the Ad26.ZEBOV (dose 1) followed by MVA-BN-Filo (dose 2) 56 days later, by monitoring adverse events (AEs) following the booster vaccination and by assessing binding antibody responses using the Filovirus Animal Non-Clinical Group (FANG) Enzyme-Linked Immunosorbent Assay (ELISA).

Primary Objectives

- To assess the safety and tolerability of a booster dose of Ad26.ZEBOV at a dose of 5×10^{10} viral particles (vp) in children previously vaccinated with the Ad26.ZEBOV, MVA-BN-Filo vaccine regimen with a 56-day interval.
- To assess vaccine-induced humoral immune responses to the Ebola virus glycoprotein (EBOV GP), as measured by FANG ELISA, at 7 and 21 days following a booster dose of Ad26.ZEBOV at a dose of 5×10^{10} vp in children previously vaccinated with the Ad26.ZEBOV, MVA-BN-Filo vaccine regimen with a 56-day interval.

Exploratory Objectives

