4.1 INCLUSION CRITERIA

Each potential participant must satisfy all of the following criteria to be enrolled in this current study:

1. Child must be enrolled in the VAC52150EBL3005 (EBOVAC-Salone Extension) study but not in the immunogenicity subset of EBOVAC-Salone Extension study.
2. Child must be a former participant in the VAC52150EBL3001 (EBOVAC-Salone) trial, and have received Ad26.ZEBOV (dose 1) vaccination followed by the MVA-BN-Filo (dose 2) vaccination within the EBOVAC-Salone trial window for dose 2 vaccination.
3. Child must have been aged 1 to 11 years old at the time of dose 1 vaccination in the EBOVAC-Salone trial.
4. The parent/guardian must consent for their child to participate in the VAC52150EBL2011 study by signing (or thumb printing, if illiterate) an ICF, indicating that he or she understands the purpose of, and procedures required for, the study, understands the potential risks and benefits of the study, and is willing to allow their child to participate in the study. If the parent/guardian cannot read or write, the procedures must be explained, and informed consent must be witnessed by a literate third party not involved in the conduct of the study. Children aged 7 years and older will be asked to give positive assent for their participation in the study and the assent procedure must be witnessed by an adult, literate parent/guardian/third party not involved in the conduct of the study, and documented.
5. The parent/guardian is willing/able to ensure that their child adheres to the prohibitions and restrictions specified in this protocol (see Section 4.3)

6. Child must be healthy in the investigator's clinical judgement (and the parent/guardian's judgement) on the basis of medical history, physical examination, vital signs, and a haematological assessment (i.e. full blood count) performed at screening. Subjects must meet the following haematology parameters within 28 days before Day 1:
 - Haemoglobin ≥ 8.0 g/dL for children aged 1 to <5 years, ≥ 9 g/dL for children aged 5 or older
 - Platelet count $\geq 100 \times 10^9$ /L
 - White blood cell count $\geq 5.0 \times 10^9$ /L

Note: The haematological assessment at screening is to be performed within 28 days prior to vaccination on Day 1 and may be repeated if it falls outside this time window.

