Toxicity Grading Scale for Healthy Paediatric Participants (older than 3 months) Enrolled in Preventive Vaccine Clinical Trials

Adapted from: DMID° Pediatric Toxicity Tables (November 2007, draft). For adverse events not included in the tables below, refer to the severity criteria guidelines in section 11.1.3 Severity Criteria. Local lab references take preference over the DMD table and the different grades.

The abbreviations used in the following tables are: LLN: lower limit of normal; IV: intravenous; ULN: upper limit of normal.

LOCAL REACTIONS				
	Grade 1	Grade 2	Grade 3	Grade 4
Tenderness	Mild discomfort to touch; minimal to no limitation of use of limb	Notable discomfort to touch; Greater than minimal limitation of use of limb	Significant discomfort at rest; Severe limitation of use of limb	Hospitalization or ER visit for treatment
Erythema	<10 mm	10-25 mm	26-50 mm	>50 mm or any grade 3 with hospitalization or ER visit for treatment
Swelling	<10 mm	10-25 mm	26-50 mm	>50 mm or any grade 3 with hospitalization or ER visit for treatment

HEMATOLOGY				
	Grade 1	Grade 2	Grade 3	Grade 4
Hemoglobin for children greater than 3 months and less than 2 years of age	9.0-9.9 gm/dL	7.0-8.9 gm/dL	<7.0 gm/dL	Cardiac Failure secondary to Anemia
Hemoglobin for children greater than 2 years of age	10.0-10.9 gm/dL	7.0-9.9 gm/dL	<7.0 gm/dL	Cardiac Failure secondary to Anemia
Absolute Neutrophil Count	750-1200/mm³	400-749/mm³	250-399/mm³	<250/mm³
Platelets	75,000-99,999/mm³	50,000-74,999/mm³	25,000-49,999/mm³	<25,000/mm³
Prothrombin Time (PT)	1.1-1.2 x ULN	1.3-1.5 x ULN	1.6-3.0 x ULN	>3.0 x ULN
Partial Thromboplastin Time (PTT)	1.1-1.6 x ULN	1.7-2.3 x ULN	2.4-3.0 x ULN	>3.0 x ULN

GASTROINTESTINAL				
	Grade 1	Grade 2	Grade 3	Grade 4
Bilirubin (Fractionated bilirubin test must be performed when total bilirubin is elevated)				
Bilirubin for children greater than 3 months of age (when accompanied by any increase in other liver function test)	1.1- <1.25 x ULN	1.25- <1.5 x ULN	1.5-1.75 x ULN	>1.75 x ULN
Bilirubin for children greater than 3 months of age (when other liver functions are in the normal range)	1.1- <1.5 x ULN	1.5- <2.0 x ULN	2.0-3.0 x ULN	>3.0 x ULN
AST (SGOT)	1.1- <2.0 x ULN	2.0- <3.0 x ULN	3.0-8.0 x ULN	>8.0 x ULN
ALT (SGPT)	1.1- <2.0 x ULN	2.0- <3.0 x ULN	3.0-8.0 x ULN	>8.0 x ULN
GGT	1.1- <2.0 x ULN	2.0- <3.0 x ULN	3.0-8.0 x ULN	>8.0 x ULN
Pancreatic Amylase	1.1- 1.4 x ULN	1.5- 1.9 x ULN	2.0-3.0 x ULN	>3.0 x ULN

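### The planned laboratory table counts only worsening of toxicity grade, so a haemoglobin fall within Grade 2, where some children may enter, is not shown; add a change-from-baseline summary

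*SAP*

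**What the plan says.** Four parts of the plan combine here.

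- **Entry.** Protocol section 4.1, criterion 6, requires "Haemoglobin ≥ 8.0 g/dL for children aged 1 to <5 years" and "≥ 9 g/dL for children aged 5 or older".
- **Grading.** Protocol Appendix 1 and SAP Attachment 2 carry the same row, "Hemoglobin for children greater than 2 years of age": Grade 1 is 10.0-10.9, Grade 2 is 7.0-9.9 and Grade 3 is below 7.0 g/dL.
- **What counts.** SAP section 6.2: an abnormality, which may be a toxicity grade or a normal-range category, "will be considered as emerging in a particular period if it is worse than baseline value". A result inside local normal limits is reset to Grade 0.
- **What is tabulated.** SAP section 6.2.1: "Tabulation of the highest emerging graded abnormalities per period and overall will be provided". Tables of values below or above the normal range are reserved for tests without a grade, so haemoglobin gets no second table.

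SAP section 6 defines the safety baseline as the last value before the booster. The Time and Events Schedule places full blood counts at screening, Day 8 and Day 22, with no other laboratory safety test after the booster. Section 6.2.1 also says that the data are summarised by type of test, but names no statistic for observed values or for change.

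**The concern.** A rule based on change of grade is only as fine as the grade bands. The Grade 2 haemoglobin band is 2.9 g/dL wide, and the entry criteria let children start inside it. For such a child the table registers nothing until the value drops below 7.0 g/dL. Yet it registers a trivial fall in a child who starts just above the band.

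Safety is a primary objective, and the blood count is the only laboratory evidence on it. With about 50 children, a report that few or no emerging haemoglobin abnormalities occurred would be hard to interpret, because it would not separate stable values from falls within the band. SAP section 6.3 plans mean, SD, median, quartiles and range per time point for the children's vital signs. The blood counts have nothing comparable.

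The wording adds a smaller problem. The rule compares an abnormality with a baseline value, so one programmer could compare grades and another could compare measured results.

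**Working it through.** The documents state no computed figure on this point and the sample is one of convenience, so there is no figure to reproduce. The check is a comparison of bands.

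**Which age row applies.** Protocol section 4.1: "Child must have been aged 1 to 11 years old at the time of dose 1 vaccination". The synopsis puts the earlier vaccination more than 2 years back. Age at booster is therefore more than 1 + 2 = 3 years, and the over-2-years row applies to everyone.

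**Who can start in Grade 2.** Overlap of the entry floor with 7.0-9.9:

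- under 5 years: 8.0-9.9 g/dL
- 5 years or older: 9.0-9.9 g/dL

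Children in the 4-11 cohort are at least 4 + 2 = 6 years old at booster. The range 8.0-8.9 is thus open only to the under-5s, all of whom are in the 1-3 cohort.

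**Largest uncounted fall.** For a baseline in Grade 2, uncounted fall = baseline - 7.0:

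| Baseline (g/dL) | Lowest value still Grade 2 | Uncounted fall | Share of baseline |
|---|---|---|---|
| 8.0 (under 5 only) | 7.0 | 1.0 | 12.5% |
| 9.0 | 7.0 | 2.0 | 22% |
| 9.9 | 7.0 | 2.9 | 29% |

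In contrast, 10.0 to 9.9 is a fall of 0.1 g/dL into Grade 2 and counts as emerging. Within Grade 1 the largest uncounted fall is 10.9 - 10.0 = 0.9.

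**Dependence on the local lower limit of normal (LLN).** Values at or above the local LLN become Grade 0, so the top of the Grade 2 band is cut off when the LLN is below 10.0. The documents do not give the LLN; the values below are assumptions.

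| Assumed LLN (g/dL) | Highest Grade 2 baseline | Maximum uncounted fall within Grade 2 |
|---|---|---|
| 10.0 or more | 9.9 | 2.9 |
| 9.5 | 9.4 | 9.4 - 7.0 = 2.4 |
| 9.0 | 8.9 | 8.9 - 7.0 = 1.9 (under 5 only) |

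At an LLN of 9.0 no eligible child aged 5 or older starts in Grade 2. The contrast with 10.0 to 9.9 also needs an LLN of at least 10.0, since with a lower limit both values are Grade 0.

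**The other reading.** If the rule compares measured values, any fall within Grade 2, such as 9.9 to 9.8, is emerging and the gap closes, at the price of counting trivial changes. The grade reading is the natural one: the subject of the sentence is a grade or category, and the next sentence speaks of shifts between categories.

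**The case against.** The strongest reply is that a large fall would not pass unseen. Protocol section 10.4 lists the most severe laboratory abnormalities after vaccination, not only emerging ones, and SAP section 3 says that the protocol's planned analysis is unchanged. Protocol section 8.3.1 has the investigator review each report and record clinically relevant changes as adverse events, which are then tabulated. This stands. A reader might infer that a fall of 2.9 g/dL would go undetected in the trial, and the documents do not support that. The gap is in the summary tables: a listing shows the worst value without summarising change, and adverse event reporting rests on judgement.

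A reader might also infer that the loss is greatest in the children with least reserve. The arithmetic runs the other way: the widest uncounted fall belongs to a child at 9.9, and a child at the 8.0 floor can fall only 1.0 uncounted.

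Three further replies have some force.

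- SAP section 2 has a general rule for summarising continuous variables where appropriate. Section 6.2.1 does not carry it over, and section 2 does not name laboratory data among those shown per time point.
- The masking is shown for haemoglobin only. Platelets must be at least 100 × 10⁹/L at entry and Grade 1 starts just below that, so a child who meets the criterion starts ungraded. The other counts belong in the added summary for completeness, not because the same gap has been shown for them.
- Grade-worsening tables are a legitimate choice, and a mean change can hide one child's fall. That is a reason to include extremes and an individual plot, not to omit change altogether.

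**Conclusion.** The point holds as a limit on what the planned table can show. Followed as written, the grade rule leaves uncounted a haemoglobin fall of up to 1.0 g/dL from 8.0, 2.0 from 9.0 and 2.9 from 9.9. This rests on the grade reading of the rule and on a local LLN of at least 10.0 g/dL. With a lower limit the maximum shrinks to 2.4 (LLN 9.5) or 1.9 (LLN 9.0, under-5s only).

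How many children this touches cannot be stated, because the documents give no haemoglobin distribution for this population. Neither document says that it will conclude an absence of haematological effect, so the risk lies in how an empty or sparse table would be read, not in a stated claim. This is a cheap improvement, not an error that undermines the trial.

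**What to change.** Add to SAP section 6.2.1:

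> Haemoglobin, platelets, WBC and neutrophils will also be summarised by age group as observed values and as change from baseline (last value before the booster) at Day 8 and Day 22: n, mean, 95% CI, minimum and maximum. An individual before/after plot will be provided.

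Add to SAP section 6.2:

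> Worse than baseline means a worse toxicity grade, or a worse normal-range category for ungraded tests, than at baseline.

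The reference should be the section 6 baseline, not simply the screening value, because retesting and rescreening are allowed and the two can differ. The minimum and maximum change and the plot keep a single child's fall visible.

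The cost is one more table and one more figure to review, from data already collected. No eligibility criterion or clinical rule changes.
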